5.1.1. Disrupted Dopamine Systems in Tourette's Syndrome

The underlying mechanism responsible for TS is unknown. Although the disease tends to run in families, there have been no definitive genetic mutations identified.⁴ Research to date has indicated that dopamine circuits in the central nervous system (CNS) are intimately involved based on the following observations.^{5,6,7}

- Dopamine-rich areas of the brain (e.g., striatum) are believed to control motor tics.
- Clinical neuroimaging studies of TS patients implicate dopamine-rich brain areas.
- Dopamine antagonists can ameliorate tics.

• Catecholamine depletors (e.g., tetrabenazine) can ameliorate tics.

5.2. Background on Ecopipam

Please refer to the Investigator's Brochure for more detailed information about the known benefits and risks of ecopipam.

5.2.2. Clinical Data

5.2.2.1. Safety in Humans

Clinical Summary: Legacy Schering-Plough Studies in Indications other than TS

The earlier clinical program for ecopipam conducted by Schering-Plough investigated the safety and effectiveness of ecopipam for the treatment of obesity, cocaine addiction, and schizophrenia in adults. These comprised 30 Phase 1 studies; seven Phase 2 pilot studies, 5 in subjects with schizophrenia and 2 (including 1 extension study) in subjects with cocaine addiction; and 1 completed Phase 2 and 3 discontinued Phase 3 studies in subjects with a primary diagnosis of moderate to severe obesity.

The Phase 1 studies examined ecopipam's pharmacokinetics, pharmacodynamics, bioavailability, distribution, food-effects on absorption, interactions with other drugs, bioequivalence of different

formulations, and various physiological effects in cocaine users, smokers, or healthy subjects. The results of these studies demonstrate that ecopipam was well-tolerated with no clinically significant changes in physical examinations, vital signs, electrocardiograms (ECGs), laboratory tests, electroencephalograms (EEGs), neurological examinations, or liver function tests (LFTs). Most of the reported AEs were mild to moderate in intensity. The most commonly reported AE in Phase 1 clinical studies were somnolence. Other commonly reported AEs in Phase 1 clinical studies were headache, fatigue, nausea, and insomnia.

In a Phase 2 study (C197-184), 279 subjects with cocaine dependence in 3 dose groups (10-, 25-, and 100 mg/day) were exposed to ecopipam HCl for 8 weeks in a placebo-controlled study. No differences in the reduction of cocaine use were demonstrated in favor of ecopipam compared with placebo. The most common AEs reported among all subjects in the cocaine addiction studies were fatigue, headache, nausea, insomnia, and somnolence. Fatigue and somnolence appeared to be reported more often in subjects treated with ecopipam than placebo. Somnolence appeared to occur in a dose-related fashion, occurring in 28% (26/94), 31% (29/94), 43% (39/91), and 20% (19/93) of subjects treated with ecopipam HCl 10-, 25-, and 100 mg/day, and placebo, respectively.

Five open-label safety, tolerability and Phase 2 studies of ecopipam in 56 subjects with schizophrenia were conducted. Subjects diagnosed with acute schizophrenia, schizophreniform disorder, or bipolar schizoaffective disorders were treated with ecopipam HCl up to a daily dose of 600 mg. The maximum duration of treatment was 6 weeks. Ecopipam, when administered to subjects with schizophrenia, did not demonstrate efficacy in these studies. The most commonly reported AEs were somnolence (21%, 12/56), headache, nausea, vomiting, and dizziness (each reported in 14%, 8/56 subjects), insomnia (9%, 5/56), dyspepsia (7%, 4/56), and anxiety (7%, 4/56).

In a Phase 2, double-blind, placebo-controlled study (C/I98-271), 185 subjects with a primary diagnosis of moderate to severe obesity were treated with ecopipam HCl (10-, 30-, or 100 mg PO, once per day) for 12 weeks. Subjects receiving ecopipam HCl showed a dose-dependent weight loss. The most commonly reported AEs by subjects receiving ecopipam HCl were headache, 19% (36/185); viral infection, 19% (36/185); somnolence, 18% (34/185); insomnia, 9% (17/185); and nausea, 9% (16/185).

In three Phase 3, double-blind, placebo-controlled studies (P00359, P00396, and P00741), obese subjects including type 2 diabetic subjects were treated with ecopipam HCl (50 or 100 mg PO, once daily [QD]) for 52 weeks. Subjects receiving ecopipam HCl showed a dose-dependent weight loss. These Phase 3 studies were discontinued because of unexpected psychiatric AEs (ecopipam 31% vs. placebo 15%), including depression, anxiety, and suicidal ideation, thereby excluding its projected use in weight management. The most frequently reported AEs in all Phase 3 obesity studies receiving ecopipam HCl were upper respiratory tract infection 30% (439 of 1482 subjects reporting), insomnia 17% (248/1482), headache 16% (244/1482), depression 16% (236/1482), somnolence 15% (216/1482), fatigue 15% (215/1482), anxiety 14% (211/1482), pharyngitis 9% (137/1482), back pain 8% (114/1482), and nausea 7% (107/1482). The frequencies of insomnia, depression, somnolence, and anxiety were about twice as frequent in subjects receiving ecopipam HCl than placebo. The frequencies of upper respiratory tract infection, headache, fatigue, pharyngitis, back pain and nausea were similar in frequencies in subjects receiving ecopipam and placebo.

Clinical Summary: Psyadon Studies in Indications other than TS

Following acquisition of ecopipam by Psyadon from Schering-Plough, two Phase 1 studies, one study in Lesch-Nyhan Disease (LND) subjects aged ≥6 years old (PSY101) and one study of the pharmacokinetics of ecopipam controlled release capsules in male adult volunteers (PSY401), were completed.

One Phase 2a study in adult subjects with pathological gambling (PSY201) was also completed. In addition, a Phase 3, multicenter, randomized, double-blind, 3-period crossover study with an open-label extension in subjects with LND (\geq 6 years old) (PSY102) was discontinued before completion for financial (non-safety related) reasons.

In the Phase1 LND study (PSY101), in which 4 of 5 subjects were children, the most commonly reported AEs were sedation (3 subjects), dystonia (2 subjects) and nausea (2 subjects).

In a Phase 2a, single-blind (the subjects were blinded to treatment assignment), nonrandomized study, 28 subjects with pathological gambling (PSY201) received placebo (1-2 tablets/day orally depending on their urge to gamble) for 1 week and then ecopipam HCl (1-2 50-mg tablets/day orally depending on their urge to gamble) for 6 weeks. The most commonly reported AEs (incidence \geq 5%) were drowsiness (11%), fatigue (11%), anxiety (11%), vomiting (11%), headache (7%), fever (7%), depression (7%), and rhinorrhea (7%).

In a Phase 2b multicenter, double blind, randomized, crossover study (PSY302), 40 children/adolescents (ages 7-17 years) were given ecopipam HCl up to 50 mg/day (if <75 lbs) or 100 mg/day (if >75lbs) for 4 weeks. The primary endpoint was the YGTSS Total (MP) Scores which were the sum of the motor and phonic subscales of YGTSS. In the Intent-to-treat (ITT) population, the mean (± standard deviation [SD]) YGTSS Total (MP) Scores at baseline were 32.8 (±7.1) prior to ecopipam treatment and 33.7 (±6.7) prior to placebo treatment. On Day 16 of the treatment period, YGTSS Total (MP) Scores decreased by 5.1 (±8.5) points on ecopipam and 2.1 (±4.7) points on placebo. On Day 30, YGTSS Total (MP) Scores decreased by 5.6 (±8.7) points on ecopipam and 3.4 (±5.8) points on placebo. Similar results were observed in the Evaluable population.

In the ITT population, least square (LS) means (±standard error [SE]) of the difference between ecopipam and placebo treatment were -2.8885±1.5282 (95% confidence interval [CI]: -5.9822, 0.2053, p=0.0664) on Day 16 and -2.1366±1.6551 (95% CI: -5.4871, 1.2139, p=0.2045) on Day 30. The treatment difference was more obvious in the Evaluable population for both days (on Day 16, p=0.0155, and on Day 30, p=0.0435).

With respect to secondary endpoints, the changes of subscale scores were similar to YGTSS Total (MP) Scores results. The secondary endpoints were not ranked in a hierarchical order and multiplicity was not taken into account. In the ITT population, the mean (\pm SD) motor, phonic, impairment, and global scores (the sum of motor, phonic and impairment scores) at baseline were 18.4 (\pm 3.3), 14.4 (\pm 4.9), 28.0 (\pm 10.7), and 60.8 (\pm 16.5) prior to ecopipam; and 18.3 (\pm 3.4), 15.4 (\pm 4.5), 27.5 (\pm 9.3), and 61.2 (\pm 14.0) prior to placebo, respectively. After 30 days of treatment, the decreases in scores compared to baseline were 3.3 (\pm 4.2), 2.3 (\pm 4.9), 7.0 (\pm 11.6), and 12.6 (\pm 18.7) on ecopipam; and 1.6 (\pm 3.3), 1.8 (\pm 3.6), 3.0 (\pm 9.1), and 6.4 (\pm 13.4) on placebo, respectively. Similar results were observed in the Evaluable population.

In the ITT population, after 30 days of treatment, Clinician Global Impression (CGI) Severity Scores decreased by $0.8~(\pm0.7)$ points on ecopipam and $0.2~(\pm0.9)$ points on placebo. Also, after ecopipam treatment, the percentages of subjects with much improved, minimally improved, no change, minimally worse CGI Improvement ratings were 40.00%, 15.00%, 20.00%, and 12.5%, respectively; while the percentages on placebo were 20.00%, 27.50%, 32.50%, and 12.50%, respectively. Similar results were observed in the Evaluable population. These data suggest that the subjects' disease severity decreased and that they had greater improvement while on ecopipam.

In the ITT population, the mean (\pm SD) DuPaul ADHD rating scale at baseline was 20.2 (\pm 11.6) points prior to ecopipam and 22.1 (\pm 11.3) points prior to placebo. On Day 30, ADHD Scores decreased by 1.9 (\pm 5.2) points on ecopipam and 2.7 (\pm 6.6) points on placebo. ADHD scales were almost unchanged after ecopipam treatment. Similar results were observed in the Evaluable population.

In the ITT population, the mean (\pm SD) YBOCS total scores at baseline were 5.7 (\pm 6.3) prior to ecopipam and 6.6 (\pm 6.9) prior to placebo. On Day 30 of the treatment period, YBOCS total scores decreased by 0.8 (\pm 3.3) points on ecopipam and 0.9 (\pm 4.1) points on placebo. The results of the obsession and compulsion subscales were similar to the total scores.

The results from the Safety population were the same as the ITT population.

A total of 149 treatment-emergent adverse events (TEAEs) were reported in 35 of the 40 treated subjects (87.50%). There was 1 serious TEAE during placebo treatment and 1 TEAE resulting in dose withdrawn permanently during ecopipam treatment. More patients on placebo had severe adverse events (7.5%) compared to ecopipam (5%). No TEAE resulted in death. There were 20 subjects (50.00%) reporting TEAEs related to study drug during ecopipam treatment and 10 subjects (25.00%) during placebo treatment. Forty percent (40.00%) of TEAEs were mild and 37.50% were moderate. One subject decreased the dosage due to fatigue one day after starting ecopipam. Another subject in the ecopipam group was discontinued from the study due to rash starting at Day 0 of the second treatment phase.

The most common TEAEs during ecopipam treatment were headache (6 of 40), abdominal pain upper (4 of 40), nausea (4 of 40), vomiting (4 of 40), insomnia (4 of 40), and somnolence (4 of 40). The most common TEAEs during placebo treatment were nasopharyngitis (5 of 40), headache (5 of 40), abdominal pain upper (4 of 40), and diarrhea (4 of 40). The most common related TEAEs during ecopipam treatment were nausea (4 of 40) and somnolence (4 of 40). The most common related TEAEs during placebo treatment were headache (3 of 40), somnolence (2 of 40), and initial insomnia (2 of 40).

There was no evidence that administration of ecopipam affected weight, Children's Depression Inventory (CDI) scores or Columbia Suicide Severity Rating Scale (C-SSRS) in the subjects. There were no clinically significant laboratory abnormalities, changes in vital signs, ECG, or physical examination findings after ecopipam administration. There were no AEs related to extrapyramidal reactions.

5.3. Risk-Benefit Assessment

A consideration of the potential of risks that TS subjects may be exposed to, approaches to reducing any such risks, and the possible benefits that they may derive from their participation in EBS-101-OL-001 is outlined below.

5.3.1. Assessment of Risk

As 2651 human subjects have been exposed to single and multiple doses ecopipam and safety data including collection of adverse events, physical examinations, laboratory tests, ECGs etc. have been systematically collected, there exists a fair body of information to base the understanding of potential risks and approaches to minimizing them in current and future studies.

Of the 2651 human subjects that have been exposed to ecopipam, 540 adults have participated in studies to investigate the safety, tolerability, pharmacodynamics and pharmacokinetics of ecopipam after single and multiple dose administration. Of the 2651 human subjects that have been exposed to ecopipam, a total of 2058 adult subjects have received treatment with ecopipam in therapeutic studies, including 1667 with obesity, 279 with cocaine addiction, 56 with schizophrenia, schizoaffective disorder and schizophreniform disorder, 28 with pathological gambling, 1 adult with LND, 18 adults with TS, 40 children/adolescents with TS and 9 adults with stuttering. These have shown that ecopipam is generally well tolerated with the adverse events affecting primarily the CNS (e.g., sedation, insomnia, psychiatric changes such as

depression, anxiety and suicidal ideation) and the gastrointestinal system (e.g., nausea and vomiting).

In subjects with TS, ecopipam has been evaluated in two studies, one study in adult subjects with TS and one study in children/adolescents with TS. In the pediatric TS study, overall, adverse events were more common in ecopipam compared to placebo. There were no serious adverse events (SAEs) and only one subject discontinued treatment due to an adverse event in the ecopipam group. Most adverse events were mild to moderate in severity. Adverse events in the Psychiatric Disorders, Central Nervous System Disorders and Gastrointestinal Disorders categories were more common with ecopipam than placebo. Notably, more subjects experienced adverse events of somnolence, insomnia, sedation, restlessness, irritability, nausea and vomiting with ecopipam than with placebo. There were no AEs of extrapyramidal symptoms in the pediatric study. A higher percentage of subjects on ecopipam gained 5 pounds or more during the study than with placebo (17.5% compared to 15%). Orthostatic blood pressure assessments were not done (or not reported). A table of weight changes was provided for the open-label extension study (PSY302A) and almost all of the children gained weight after 3, 6, 9 or 12 months of treatment. Suicidal ideation was seen both during the blinded study as well as the open-label extension study in pediatric subjects on ecopipam. There did not appear to be clinically significant ECG findings. However, open-label extension adverse event data have not yet been analyzed.

In the adult study in TS, the most commonly reported adverse events (incidence \geq 20%) were sedation (33%), insomnia (33%), fatigue (33%), somnolence (28%), headache (22%), muscle twitching (22%) and anxiety (22%). Two subjects developed adverse event of akathisia and one developed an adverse event of tremor, both of which are extrapyramidal reactions. Three of 18 subjects (16.7%) also discontinued study drug due to an adverse event.

For the older obesity and cocaine dependence program, there were subjects who experienced adverse events of weight gain, suicidal ideation, diabetes, extrapyramidal reactions, somnolence, insomnia, hypotension and sexual side effects. There was no raw data on orthostatic blood pressure. In a table of all adverse events during the whole program, the adverse event of dyskinesia is listed but is not in any of the data tables. When reviewing the large Phase 2 and Phase 3 studies in obesity and the other indications, the rate of tardive dyskinesia appears to be extremely low (or absent) and the rate of other extrapyramidal reactions (akathisia, tremor, etc.) appears at rates that are largely less than what is seen with D1/D2 antagonists. Data for shifts in fasting glucose or lipids were not in the Investigator's Brochure prepared by a previous sponsor and comments were made that there were no significant laboratory changes. There did not appear to be a high rate of increased blood glucose or lipids in the adverse event tables for the other studies. Additionally, data on orthostatic blood pressure changes were not documented but no adverse events of orthostatic hypotension were observed.

5.3.2. Assessment of Benefit

A review of the efficacy evaluations for ecopipam in the two studies conducted in subjects with TS reveals improvement on the YGTSS scores and other measures of illness severity from baseline to end point.

In a Phase 2a, open-label, non-randomized study (PSY301), the activity and safety of ecopipam in 18 adult subjects with TS was evaluated. Subjects were to receive ecopipam HCl 50 mg for 2 weeks followed by 100 mg for 6 weeks. The primary outcome measure was the YGTSS Total (MP) score. After ecopipam treatment, the YGTSS Total score, motor tics score, phonic tics score and overall impairment decreased from baseline to endpoint, suggesting that the severity of tics was decreased (Table 16, Investigator's Brochure).

In a Phase 2b double-blind, randomized crossover study in children/adolescents (ages 7-17 years) with TS (PSY302), 40 subjects were enrolled and 38 (95.0%) completed the study. The primary endpoint was the YGTSS Total (MP) score.

Ecopipam treatment resulted in a numerical decrease in the YGTSS Total score relative to the placebo treatment, but the decrease was not statistically significant (Figure 9, Investigator's Brochure). The least squares means (±SE) of the difference between ecopipam and placebo treatment were -2.8885 (±1.5282); 95% CI: -5.9822, 0.2053, p=0.0664) on Day 16 and -2.1366 (±1.6551; 95% CI: -5.4871, 1.2139, p=0.2045) on Day 30.

Based on the available safety data, there are some safety advantages for ecopipam compared to D2 antagonists, but the full measure of differentiation will not be known until after a larger and longer Phase 3 program. The rate of tardive dyskinesia and other extrapyramidal reactions commonly associated with D2 antagonists appears much lower with ecopipam. Other possible advantages include a decreased risk of lipid changes, hyperglycemia and orthostatic hypotension.

An individual subject may not receive any therapeutic benefit from participating in an investigational study however, by contributing to medical research, others will be helped. All subjects participating in the study will receive physical examinations, various laboratory tests, ECGs and a systematic evaluation of their condition. Ecopipam may help improve symptoms for participants.

5.3.3. Methods to Minimize Risks

The following steps are incorporated in the protocol to minimize risks to subjects.

- Subjects will be screened for appropriateness to participate in this study
- All subjects will be evaluated for safety at monthly visits for one year. Follow-up visits will be conducted 7 and 14 days after the last dose of study medication and a follow-up phone call will be conducted 30 days after the last dose of study medication.
- All subjects will be evaluated using the following scales to assess possible worsening of other psychiatric symptoms or other side effects:
 - Abnormal Involuntary Movements Scale
 - Barnes Akathisia Rating Scale
 - Columbia Suicide Severity Rating Scale
 - Children's Depression Rating Scale-Revised
 - Gilles de la Tourette Syndrome Quality of Life Scale

- Pediatric Anxiety Scale
- Clinical Global Impression Tourette Syndrome of Severity

In summary, ecopipam is a new chemical entity with a novel mechanism of action that has some evidence that it may be of therapeutic benefit to subjects with TS. There is also evidence that it is likely to have lower side effect burden (for movement disorders, extrapyramidal symptoms, tardive dyskinesia, etc., metabolic syndrome and elevated prolactin) than the currently used dopamine antagonists. The protocol has processes to minimize potential risks from study medication that participants may be exposed to such that risks from the study balance the potential benefits.

6. STUDY OBJECTIVES AND PURPOSE

6.1. Primary Objective

The primary objective of this study is to evaluate the long-term safety and tolerability of ecopipam tablets in pediatric subjects (aged ≥ 6 to ≤ 18 years at Baseline) with TS that were previously enrolled in study EBS-101-CL-001 within the time period specified for this protocol.

6.2. Secondary Objectives

The secondary objective of this study is to evaluate the durability of effect of ecopipam in pediatric subjects (aged ≥ 6 to ≤ 18 years at Baseline) with TS.

7. INVESTIGATIONAL PLAN

7.1. Overall Study Design

This is an international, multicenter, open-label, long-term extension study evaluating the safety of ecopipam tablets for the treatment of pediatric subjects (aged ≥6 to ≤18 years at Baseline) with TS. Subjects who completed the Phase 2b, randomized, double-blind, efficacy and safety study (EBS-101-CL-001) and who meet all the inclusion/exclusion criteria for this study will be eligible to participate in this study. All subjects will be titrated to a target dose of 2 mg/kg/day as participants rolling over from the Phase 2b double-blind efficacy and safety study will be tapered off of study medication to maintain the blind from that study. Subjects will complete study visits every month for 1 year. A Follow Up visits will be conducted 7 and 14 days after the last dose of study medication and a Follow Up phone call will be conducted 30 days after the last dose of study medication. Study Visits may be completed in locations other than clinic and/or safety and efficacy assessments required at these visits will be made available for remote administration due to restrictions as a consequence of the COVID-19 pandemic or other qualifying event.

Safety will be monitored throughout the study at every visit by repeated adverse event (AE) monitoring, vital signs, the Columbia-Suicide Severity Rating Scale (C-SSRS), the Abnormal Involuntary Movement Scale (AIMS), the Barnes Akathisia Rating Scale (BARS), the Pediatric Anxiety Rating Scale (PARS) and Children's Depression Rating Scale-Revised (CDRS-R). In addition to these assessments, at Baseline, Months 1, 3, 6, 9 and 12 safety will also be monitored by clinical and laboratory evaluations, and electrocardiogram (ECG) monitoring. In addition to the scales aforementioned, the YGTSS, CGI Tourette Syndrome of Severity (CGI-TS-S), and Gilles de la Tourette Syndrome—Quality of Life Scale for Children and Adolescents (C&A-GTS-QOL) will also be assessed at Baseline, Months 1, 3, 6, 9 and 12. The CGI-TS-I will be conducted at Months 1, 3, 6, 9, and 12. At the Follow Up visits, AE monitoring, the C-SSRS, clinical and laboratory evaluations and vital signs will be assessed. A Follow Up phone call will be conducted 30 days after the last dose of study medication to assess AEs.

7.2. Number of Subjects

The actual number of subjects that are enrolled will depend on the final number of subjects who complete study EBS-101-CL-001.

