At the end of the 52-week treatment phase, subjects will titrate off therapy and receive ecopipam HCl doses that will be reduced by 25 mg/day until off drug.

Duration of treatment:

52-weeks, until New Drug Application (NDA) approval, or until development of the study drug is discontinued by the Sponsor, whichever is sooner.

Criteria for evaluation:

Safety: Study Visits may be completed in locations other than clinic and/or safety and efficacy assessments required at these visits will be made available for remote administration due to restrictions as a consequence of the COVID-19 pandemic or other qualifying event. Safety will be monitored throughout the study at every visit by repeated adverse event (AE) monitoring, vital signs, the Columbia-Suicide Severity Rating Scale (C-SSRS), the Abnormal Involuntary Movement Scale (AIMS), the Barnes Akathisia Rating Scale (BARS), the Pediatric Anxiety Rating Scale (PARS) and Children's Depression Rating Scale-Revised (CDRS-R). In addition to these assessments, at Baseline, Months 1, 3, 6, 9 and 12 safety will also be monitored by clinical and laboratory evaluations and electrocardiogram (ECG) monitoring. At the Follow Up visits, AE monitoring, the C-SSRS, clinical and laboratory evaluations and vital signs will be assessed. Laboratory evaluations will include hematology, chemistry, urine values and HbA1c. A Follow Up phone call will be conducted 30 days after the last dose of study medication to assess AEs. Subjects will be monitored for signs of abuse, and withdrawal or dependence.

Efficacy: The YGTSS, CGI-TS-S and C&A-GTS-QOL will be conducted at Baseline and Months 1, 3, 6, 9 and 12. The CGI-TS-I will be conducted at Months 1, 3, 6, 9, and 12.

All safety and efficacy variables will be summarized descriptively.

Additional analyses may need to be conducted for data not collected at sites and/or collected via remote administration due to restrictions as a consequence of the COVID-19 pandemic or other qualifying event, these additional analyses will be specified in the SAP.

	3	•	TABLE	OF	CON	TENTS
--	---	---	--------------	----	-----	-------

1.	PROTOCOL AMENDMENT CHANGES	2
SIGNATU	RE PAGE	10
INVESTIG	GATOR'S AGREEMENT	11
PROCEDU	JRES IN CASE OF EMERGENCY	12
2.	SYNOPSIS	13
3.	TABLE OF CONTENTS	17
4.	LIST OF ABBREVIATIONS AND DEFINITIONS OF TERMS	20
5.	INTRODUCTION	21
5.1.	Background on Tourette's Syndrome	21
5.1.1.	Disrupted Dopamine Systems in Tourette's Syndrome	22
5.2.	Background on Ecopipam.	23
Cl		

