3.1. Primary Objective

The primary objective of this study is to evaluate the long-term safety and tolerability of ecopipam tablets in pediatric subjects (aged ≥ 6 to ≤ 18 years at Baseline of the EBS-101-CL-001 study) with Tourette's Syndrome (TS) that were previously enrolled in the EBS-101-CL-001 study (Phase 2b) and completed the Phase 2b study.

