3.5. Determination of Sample Size

This is a one-year safety and tolerability study as a follow up to the double-blind study (EBS-101-CL-001) and number of subjects enrolled in this is dependent on the number of subjects completing that study.

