6.1. General Methods

All analyses and outputs will be produced using SAS® version 9.4 or later. Continuous variables will be summarized using the number of observations (n), mean, standard deviation (SD), median, minimum, and maximum. Categorical variables will be summarized using frequency counts (n), and percentages.

All relevant subject data will be included in listings. All subjects entered the database will be included in subject data listings. All by visit summaries will use the nominal visit. Unscheduled visits will not be summarized but will be included in the listings.

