12.2.5.2. Table Conventions

- Units will be included where available.
- If the categories of a parameter are ordered, then all categories between the maximum and minimum category are presented in the table, even if n=0 for all treatment groups in a given category that is between the minimum and maximum level for that parameter. For example, the frequency distribution for symptom severity would appear as:

Severity Rating	N
mild	3
moderate	8
severe	0

Where percentages are presented in these tables, zero percentages will not be presented and so counts of 0 will be presented as 0 and not as 0 (0%).

This document is confidential.

- If the categories are not ordered (e.g., Medical History, Reasons for Discontinuation from the Study, etc.), then only those categories for which there is at least 1 subject represented in 1 or more groups are included.
- An Unknown or Missing category are added to each parameter for which information is not available for 1 or more subjects.
- Unless otherwise specified, the estimated mean and median for a set of values are printed out to 1 more significant digit than the original values, and standard deviations are printed out to 2 more significant digits than the original values. The minimum and maximum should report the same significant digits as the original values. For example, for systolic blood pressure:

N	XX
Mean (SD)	XX.X (XX.XX)
Median	XX.X
Min, Max	XX, XX

- P-values are output in the format: "0.xxx", where xxx is the value rounded to 3 decimal places. Every p-value less than 0.001 will be presented as <0.001. If the p-value are less than 0.0001, then present as <0.0001. If the p-value is returned as >0.999, then present as >0.999.
- Percentage values are printed to one decimal place, in parentheses with no spaces, one space after the count (e.g., 7 (12.8%), 13 (5.4%)). Pre-determine how to display values that round down to 0.0. A common convention is to display as '<0.1', or as appropriate with additional decimal places. Unless otherwise noted, for all percentages, the number of subjects in the analysis set for the treatment group who have an observation will be the denominator. Percentages after zero counts should not be displayed and percentages equating to 100% are presented as 100%, without decimal places.

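### Safety is the primary objective, yet safety rates are planned as n (%) without intervals and event categories with no cases can drop out of the tables, so the outputs will not state which event rates the data exclude

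*Protocol*

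**What the plan says.** **Objective.** SAP 3.1: "The primary objective of this study is to evaluate the long-term safety and tolerability of ecopipam tablets in pediatric subjects". Protocol 6.1 agrees.

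**Size.** Protocol 7.2: "The actual number of subjects that are enrolled will depend on the final number of subjects who complete study EBS-101-CL-001". SAP 3.5 likewise says that the "number of subjects enrolled in this is dependent on the number of subjects completing that study". Neither gives an expected number, a range or a precision statement.

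**Safety summaries.** Protocol Synopsis: "All safety and efficacy variables will be summarized descriptively". SAP 6.1: "Categorical variables will be summarized using frequency counts (n), and percentages". The adverse event overview in SAP 9.3 and the Columbia scale (C-SSRS) summary in SAP 9.8.1 follow this pattern. The SAP plans no confidence interval. Its only inferential output is the paired t-test on efficacy scales (SAP 8.1 to 8.3).

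**Zeros.** SAP 12.2.5.2 says that "counts of 0 will be presented as 0 and not as 0 (0" (the clause ends with a percent sign). The same section keeps an unordered category only if at least one subject falls in it. Percentages by default use the subjects who have an observation as denominator.

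**Denominators.** SAP 12.2.4 prints the analysis-set N in the column heading.

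**AESIs.** Protocol 13.2.1 lists extrapyramidal reactions (tardive dyskinesia and akathisia are its examples), metabolic changes, orthostatic hypotension, suicidality, and leukopenia/neutropenia/agranulocytosis. It leaves the full description to the SAP. The two lists in SAP 9.3 do not name tardive dyskinesia, akathisia, orthostatic hypotension or agranulocytosis. Dyskinesia appears only as a single term in the Parkinsonism list.

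**The concern.** A single-arm safety study answers its question through event rates and how high the true rates could still be. Here the secondary, efficacy objective gets p-values, while event rates under the primary objective get a point estimate only.

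This matters most for rare events. For several of the protocol's AESIs, none or very few cases are likely in a cohort of ordinary size. For those the layout can remove the result: a preferred term with no cases has no row, so the report would be silent about an event that the protocol said in advance it would follow. Where a zero row does survive, as in a fixed-format by-visit table, it is a bare 0 whose denominator may differ from the N in the column heading.

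**Working it through.** **1. The plan's own figure.** There is none to reproduce. No sample size, expected event count or precision target is stated, so every N below is assumed.

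**2. Formulas.**
- Zero events in N, two-sided exact (Clopper-Pearson) 95% upper limit: 1 − 0.025^(1/N). Example: 1 − 0.025^(1/100) = 3.6%.
- x > 0 events: the limits are the 2.5% quantile of Beta(x, N−x+1) and the 97.5% quantile of Beta(x+1, N−x).
- Chance of seeing at least one case when the true rate is 1%: 1 − 0.99^N.

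**3. Results.**

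| N (assumed) | 0 events: upper limit | 1 event: 95% interval | Chance of at least 1 case at a true 1% |
|---|---|---|---|
| 50 | 7.1% | 0.05–10.65% | 39.5% |
| 100 | 3.6% | 0.03–5.45% | 63.4% |
| 150 | 2.4% | 0.02–3.66% | 77.9% |
| 200 | 1.8% | 0.01–2.75% | 86.6% |

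Read the other way, the N needed for a zero count to exclude a rate p is ln(0.025)/ln(1−p), rounded up: 72 for 5%, 122 for 3%, 183 for 2% and 368 for 1%.

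**4. Why the denominator must be the number assessed.** Suppose 20% or 40% of subjects are not assessed at Month 12 (both assumed). The zero-event upper limit for a Month 12 row becomes:

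| N enrolled | 20% missing | 40% missing |
|---|---|---|
| 50 | 8.8% (n=40) | 11.6% (n=30) |
| 100 | 4.5% (n=80) | 6.0% (n=60) |
| 150 | 3.0% (n=120) | 4.0% (n=90) |
| 200 | 2.3% (n=160) | 3.0% (n=120) |

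With 100 enrolled and 40% missing, a reader who works from the heading N obtains 3.6% where 6.0% is correct.

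**5. What the tables would show for an AESI with no cases.** The AESI tables in SAP 9.3 run by system organ class and preferred term, which are unordered categories. Under SAP 12.2.5.2 a term with no subjects is left out, so the usual result is a missing row and not a printed 0. The bare 0 applies to rows that are shown anyway. For an AESI that is in Protocol 13.2.1 but not named in SAP 9.3, an absent row cannot be told apart from an event that was never tabulated.

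**The case against.** Much of the case on the other side stands.

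- **The open N.** Enrolment in a roll-over extension is set by who completes the parent study, and both documents say so. That is not a defect.
- **A reader might infer that the trial cannot say what harm it has excluded.** The documents do not support this. N is in the column headings, counts are tabulated, and SAP 12.2.5.2 asks for denominators to be explained in notes. For a whole-Safety-Set count, anyone can work out the limit from 0/N. The statistic is not printed, but the information is not lost. The argument weakens only where the row is omitted or where the number assessed differs from the heading N.
- **A reader might infer that a zero will be used to confirm the Protocol 5.3.2 statement:** "The rate of tardive dyskinesia and other extrapyramidal reactions commonly associated with D2 antagonists appears much lower with ecopipam". That sentence describes earlier data, and the one before it defers full differentiation to a larger and longer Phase 3 program. The documents do not plan to use this study that way.
- **A reader might want the depression rate here set against the earlier obesity program,** of which Protocol 5.2.2.1 says: "The frequencies of insomnia, depression, somnolence, and anxiety were about twice as frequent in subjects receiving ecopipam HCl than placebo". No such comparison is planned and those were obese subjects in another indication, so this point does not rest on it.
- **Uncertainty is not wholly absent.** The AIMS, BARS, CDRS-R and PARS scores, laboratory values, vital signs and ECG intervals are continuous, and SAP 6.1 gives them n, mean, SD, median and range.
- **Safety was declared descriptive, with no threshold to exclude.** True, but a confidence interval is itself descriptive. It needs no hypothesis and no multiplicity control.

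**Conclusion.** The point holds as a reporting gap in the primary objective, not as a flaw in the design or a loss of data. As planned, the outputs will not state the event rate that the data exclude, and an AESI named in advance may not appear at all if it has no cases.

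The size depends on a cohort size that the documents do not give. Over an assumed N of 50 to 200, a zero count leaves true rates of up to 7.1% down to 1.8% compatible with the data (two-sided exact 95%), and more where fewer subjects are assessed. The limits are binomial and count each subject once. The missingness figures are illustrations.

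The change is worth making because it is nearly free and bears on the main purpose of the study.

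**What to change.** 1. **Intervals.** In SAP 9.3, 9.6 and 9.8.1 add two-sided Clopper-Pearson 95% intervals to the subject-level rates of serious adverse events, adverse events leading to discontinuation, each AESI group, C-SSRS ideation and behaviour, and QTc outliers.
2. **Forced rows.** Override SAP 12.2.5.2 so that every AESI category in Protocol 13.2.1 and in SAP 9.3 has a row whether or not a case occurred. Show zero as 0/N with its upper limit, where N is the number of subjects assessed for that row. Because the AESI tables run by organ class and preferred term, this means adding group-level rows. It also means specifying the terms for the protocol categories that SAP 9.3 does not name. Without that step, intervals for the SAP's AESI groups would still miss tardive dyskinesia, akathisia, orthostatic hypotension and agranulocytosis.
3. **Labelling.** SAP section 10 already records analyses added after database lock. If these intervals are added now, label them the same way and do not present them as prospective precision planning.

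**Cost.** SAP wording, one extra column, some forced rows and a term list; no new data. Low and zero rates will look less favourable once their upper limits are printed.
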